## **10 EFFICACY ANALYSIS**

Efficacy analysis will be performed after the last patient has completed the study. Data to be included in this analysis include Subject Disposition, Extent of Drug Exposure, Demographic and Baseline Characteristics, Primary Outcome (MITT & PP population, LOCF & OC), all secondary efficacy endpoints (MITT, LOCF), OCT-A (MITT, LOCF & OC), UACR (MITT & PP population, LOCF & OC), eGFR (MITT & PP population, LOCF & OC), ERG (MITT, LOCF & OC), and UWF-FA (MITT, LOCF & OC). The primary efficacy analysis will only contain data on events that occurred at timepoints up to and including the EOT visit (week 48).

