### 7.1 Missing Data

Efficacy data related to eye anatomy or visual function that is collected after rescue treatment (i.e., treatment for DME or PDR other than study medication) will be treated as missing data. Unless, otherwise stated, missing data will be handled using the following approach:

- For start date, partial dates will have first day of the month imputed if day is missing, and January of that year will be imputed if month is missing. If both day and month are missing, January 01 will be imputed.
- For end date, partial dates will have last day of the month imputed if day is missing, and December of that year will be imputed if month is missing. If both day and month are missing, December 31 will be imputed.
- Missing data are imputed using Last Observation Carried Forward (LOCF) for all visits except screening/baseline; screening/baseline values are not carried forward.
- For vision related efficacy measurements (Tables 14.2.1.x, 14.2.2.x, 14.2.3.x, 14.2.4.x, 14.2.5.x, 14.2.6.x, 14.2.7.x, 14.2.8.x, 14.2.10.x, 24.2.11.x, 14.2.12.x, 14.2.13, 14.3.12.3, 14.3.13.3, 14.3.14.2x, 14.3.14.5) subjects receiving rescue treatment will be handled differently to reflect their status as a treatment failure and to avoid confounding of the effects of rescue treatment with the effects of study drug. Specifically, last pre-rescue data are carried forward for LOCF analysis. If rescue and DRSS occur on the same day, DRSS from that day is carried forward. For Observed Case (OC) analyses, results post-rescue are omitted, and last pre-rescue data are carried forward. Note that for DRSS scales involving both eyes (Person and Binocular scale) the carry forward rules apply only to the rescued eye in calculation of the combined score.
- Where severity or relationship is missing for adverse events, most conservative imputation will be made.

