## **10.2 Secondary, Exploratory and Exploratory Sub-Study Efficacy Endpoint Analysis**

Secondary efficacy endpoints are summarized in Section 5.2, and involve alternative analyses of DRSS results, showing the proportion of patients who develop sight-threatening complications of DR (DME & PDR). Measures of kidney function (UACR and eGFR) are exploratory efficacy endpoints. Exploratory sub-study endpoints are derived from OCT-Angiography, Ultra-wide field fluorescein angiography, Ultra-wide field color photographs, and electroretinography. Details of these variables and their analysis are contained in separate SAPs.

Normality assumption will be tested for any endpoint of continuous nature. If normality assumption is violated, appropriate transformation and/or non-parametric analysis will be employed. Otherwise, all secondary, exploratory and exploratory sub-study endpoints of continuous nature will be analyzed using ANCOVA model, and all inferential analyses will use a 2-sided 5% significance level. For the exploratory efficacy endpoints UACR and eGFR, for internal decision-making purposes, a 1-sided 10% significance level will be used. Whenever possible, a mixed model repeated measures (MMRM) model will be utilized to analyze this data. The model will include change from baseline as the dependent variable. The p-value and 95% CI from the model is baseline parameter adjusted.

For MMRM, visit will be treated as the repeated variable within a subject. Within-subject error, an unstructured variance-covariance will be applied; in case of non-convergence, compound symmetry will be used. MMRM model for UACR and eGFR is adjusted by the baseline HbA1c, Baseline Systolic BP, log-transformed Baseline UACR, and ACEi/ARB use.

Secondary, exploratory and exploratory sub-study endpoints of a dichotomous nature will be analyzed using the same approach as outlined for the primary efficacy endpoint.

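### Mean change in DRSS is listed for LOCF analysis only, although the SAP also calls for an MMRM; the SAP should fit that model to observed data and say which endpoints it covers

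*SAP*

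**What the plan says.** Four places bear on this.

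- **SAP 10 (Efficacy Analysis)** lists the analyses by endpoint group. The secondary endpoints appear as "all secondary efficacy endpoints (MITT, LOCF". The primary outcome, OCT-A, ERG, UWF-FA, eGFR and UACR each get both data sets, for example "UACR (MITT & PP population, LOCF & OC".
- **SAP 7.1 (Missing Data)** gives the general rule: "Missing data are imputed using Last Observation Carried Forward (LOCF) for all visits except screening/baseline; screening/baseline values are not carried forward". For rescued eyes it adds: "For Observed Case (OC) analyses, results post-rescue are omitted, and last pre-rescue data are carried forward".
- **SAP 10.2** sets the base model: "endpoints of continuous nature will be analyzed using ANCOVA model, and all inferential analyses will use a 2-sided 5% significance level". After a sentence on UACR and eGFR it continues: "Whenever possible, a mixed model repeated measures (MMRM) model will be utilized to analyze this data". For the within-subject error, "an unstructured variance-covariance will be applied; in case of non-convergence, compound symmetry will be used".
- **SAP 5.2** makes mean change in study-eye DRSS at Week 48 a secondary endpoint, with the secondary endpoints also assessed at Weeks 12, 24 and 36.

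Protocol 11.7 left the handling of missing secondary data to the SAP.

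**The concern.** An MMRM deals with missed visits through the likelihood of the values actually observed, and is valid if data are missing at random. If missing visits are first filled with the last value, there is nothing left for the model to handle. Each carried value then counts as a fresh measurement, and the result rests on the assumption that a subject's DRSS stays frozen after drop-out.

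This matters in this trial for two reasons. Subjects who stop study medication have their end-of-treatment assessments early and then only a one-month follow-up (Protocol 7.6), so their later DRSS visits are missing by design. Fundus photographs are scheduled every three months (Protocol Appendix A), so one carried value may stand in for one or more quarterly visits.

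At stake are the Week 48 estimate and confidence interval for the mean DRSS change, the main continuous secondary endpoint.

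**Working it through.** **1. The plan's own figure.** The documents give no effect size, SD or power for a continuous endpoint. The only sample-size figure is for the primary test (SAP 3.1): 45 evaluable per arm, 30% vs 5%, two-sided 0.05. Power is the sum, over all pairs (x, y) with x > y and Fisher p ≤ 0.05, of Bin(x; 45, 0.30) × Bin(y; 45, 0.05). The result is 86.3%, which agrees with the stated figure of more than 85%. Sample size is 45/0.90 = 50 per arm. From here I take 50 per arm and the planned 10% drop-out.

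**2. Assumed inputs (not in the documents).** Visits at Weeks 12/24/36/48. SD of DRSS change 0.9/1.1/1.25/1.4 steps. Correlation 0.7 per visit lag. Negative values mean improvement. Drop-out d falls at a constant rate over the three intervals after Week 12, so the per-interval rate is h = 1 − (1 − d)^(1/3). The baseline covariate was left out.

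**3. Expected LOCF contrast.** With equal, non-informative drop-out it is Σ P(last visit = v) × effect at v. At d = 0.10, h = 0.0345 and the last-visit probabilities are 0.0345, 0.0333, 0.0322 and 0.900. For an effect growing −0.2, −0.4, −0.6, −0.8:

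0.0345(0.2) + 0.0333(0.4) + 0.0322(0.6) + 0.900(0.8) = 0.760, against a true 0.80: 5% attenuation.

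The same sum gives 0.718 (10%) at d = 0.20 and 0.675 (16%) at d = 0.30.

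**4. Simulation, 3,000 trials per scenario.** LOCF is compared with the maximum-likelihood estimate of an unstructured repeated-measures model on observed data. On filled, complete data, an unstructured MMRM with visit-specific effects gives the same Week 48 contrast as a single-visit analysis, so the LOCF column serves for both models.

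| Scenario | Drop-out | True | LOCF | Observed-data model |
|---|---|---|---|---|
| Growing | 10% | −0.80 | −0.76 | −0.80 |
| Growing | 20% | −0.80 | −0.71 | −0.79 |
| Growing | 30% | −0.80 | −0.67 | −0.80 |
| Plateau | 10% | −0.80 | −0.80 | −0.80 |
| Waning (−0.6, −0.8, −0.6, −0.4) | 10% | −0.40 | −0.43 | −0.40 |
| Waning | 20% | −0.40 | −0.45 | −0.40 |
| No effect, both arms worsen | 20% active, 5% placebo | 0 | −0.065 | −0.004 |

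The growing-effect and waning rows agree with the sum in step 3. For the last row that sum gives 0.718 − 0.780 = −0.062.

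A separate set of assumptions (1,500 trials per scenario, effect growing to 0.70, SD 0.8 rising to 1.2, correlation 0.75, drop-out depending on the last value) gave LOCF estimates of 0.67, 0.64 and 0.60 at 10/20/30% drop-out. Attenuation is 0.03/0.70 = 4%, 0.06/0.70 = 9% and 0.10/0.70 = about 14–15%, given rounding.

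**5. Standard errors, growing-effect scenario.**

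| Drop-out | LOCF model SE | LOCF sampling SD | Observed-data sampling SD | LOCF SE smaller by |
|---|---|---|---|---|
| 10% | 0.274 | 0.272 | 0.288 | 1 − 0.274/0.288 = 5% |
| 20% | 0.269 | 0.272 | 0.307 | 12% |
| 30% | 0.263 | 0.262 | 0.321 | 18% |

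With a constant SD over time the gap is 1 − 0.280/0.284 = 1% at 10% and 1 − 0.281/0.299 = 6% at 20%. With no missing data the SE is 0.279. In this scenario LOCF therefore reports slightly more precision than complete follow-up would give.

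**The case against.** **The combination is inferred.** A reader might take the SAP to say outright that the MMRM runs on LOCF data. No sentence does. SAP 10 names data sets without models, ANCOVA is the base model in 10.2, and the MMRM sentence follows one about UACR and eGFR, which do have observed-case runs. This stands as a point about wording. The narrow reading is the less likely one. Protocol 11.7 allows repeated-measures models for continuous secondary and exploratory variables generally. The OCT-A, ERG and UWF-FA sub-study plans use the same MMRM sentence with no renal context. SAP 10.2 also gives the renal MMRM its own covariates, which suggests that other MMRMs exist. If the narrow reading were right, mean DRSS change would rest on LOCF ANCOVA alone and would still lack a listed observed-data analysis.

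**Observed-case tables may exist.** SAP 7.1 gives an observed-case rule for many vision-related tables without saying which endpoints have such a version. The normality check in 10.2 could also move the discrete DRSS change to a non-parametric method. Both are possible, but SAP 10 still lists LOCF alone.

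**Attenuation is not certain.** A reader might infer that LOCF must dilute the effect. The documents give no time course for DRSS change, and the direction depends on it.

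**The standard error is not miscalibrated.** A reader might infer an inflated false-positive rate. The LOCF SE matches LOCF's own sampling SD. With no effect and equal 10% drop-out, rejection was 5.1%; in the unequal drop-out scenario it was 5.2%. The SE is small only against an analysis that acknowledges the lost information.

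**The observed-data result is partly built in.** Drop-out was simulated as missing at random or completely at random, and no rescue was simulated. Both points are fair. They limit the claim to those conditions.

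**Conclusion.** The point holds as a conflict between a stated LOCF rule and the model the SAP asks for. Followed as written, mean DRSS change is analysed only on filled data, and the main reason for choosing an MMRM is lost. The documents do not support saying that the Week 48 effect will be attenuated or that the LOCF test is invalid in its own terms.

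At the planned 10% drop-out the consequence is modest: a shift of about 5% in the effect under a growing time course, in the opposite direction under a waning one, and a standard error 1–5% below that of an observed-data model. It becomes material at 20–30% drop-out, or if drop-out differs between arms while eyes worsen. All these sizes rest on assumed SDs, correlations and time courses.

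The scope is limited to continuous secondary endpoints, which are tested without multiplicity adjustment. The primary analysis does not depend on it. Because the direction of bias cannot be known in advance and the remedy is cheap, the change should be made.

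**What to change.** In SAP 10 and 10.2:

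- State that the MMRM for continuous secondary endpoints is fitted to observed values, with no LOCF filling for drop-out or missed visits.
- Name the endpoints it covers, at least mean change in study-eye DRSS at Weeks 12, 24, 36 and 48.
- State how rescued eyes enter the model. SAP 7.1 carries the last pre-rescue value forward even in the observed-case data set, so pointing to that data set alone would still bring in carried values. If the rule is kept, label it as a treatment-failure convention, separate from the handling of missing data.
- Keep ANCOVA on LOCF data as a labelled sensitivity analysis, and add the observed-data run to the SAP 10 list.

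The cost is SAP wording and one added model run. The confidence interval may be slightly wider. No new data are needed.

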## **10.1 Primary Efficacy Endpoint Analysis**

The primary hypotheses to be tested is that AKB-9778 15 mg twice daily and AKB-9778 15 mg once daily will be superior to placebo in the improvement of DR as measured by the ETDRS severity scale change from baseline at 48 weeks. Specifically, the primary endpoint is the percentage of subjects with an improvement in study eye severity of DR (ETDRS DRSS) of  $\geq 2$  steps at 48 weeks without need for treatment of PDR or DME (by IVT, laser, or vitrectomy) in the study eye. DRSS scores used for all analyses will be obtained from final adjudicated grading by the central reading center (Fundus Photograph Reading Center for the standard field images).

The primary hypotheses will be tested in the MITT population using a Fisher's Exact Test with a 2-sided 5% significance level. AKB-9778 15 mg twice daily will be tested first. If this is found to be statistically significant, then AKB-9778 15 mg once daily will be tested for statistical significance, at the same significance level. Cochran-Mantel-Haenszel (CMH) test stratified for baseline ETDRS DRSS (levels 4, 5 and 6) will also be used for testing primary hypothesis in the MITT population. Missing data will be imputed using LOCF; baseline values will not be carried forward.

As a sensitivity analysis, primary hypothesis will be tested using Fisher's Exact test, and CMH test stratified for baseline ETDRS DRSS (levels 4, 5 and 6) on OC in the PP population.

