11.7 Efficacy Analyses

All efficacy endpoints are listed in [Sections 5.5](#) and [5.6](#). All efficacy data will be summarized by treatment group and time point using appropriate descriptive statistics. Summaries will be presented for both the MITT and PP populations. Due to the small number of subjects that are expected to be enrolled at each center, all summaries and analyses will be performed using data pooled across centers.

The primary hypotheses to be tested is that AKB-9778 15mg twice daily and AKB-9778 15mg once daily will be superior to placebo in the improvement of DR as measured by the ETDRS severity scale change from baseline at 12 months. Specifically, the primary endpoint is the

percentage of subjects with an improvement in study eye severity of DR (ETDRS DR Severity Score or DRSS) of ≥ 2 steps at Month 12 without need for treatment of PDR or DME (by IVT, laser, or vitrectomy) in the study eye. The primary hypotheses will be tested in the MITT population using a Fisher's Exact Test with a 2-sided 5% significance level. To adjust for multiplicity, a pre-specified testing order will be used. AKB-9778 15mg twice daily will be tested first, and AKB-9778 15mg once daily will be tested second. Details of how missing data will be handled for the primary endpoint, along with sensitivity analyses to assess the impact of missing data will be outlined in the statistical analysis plan (SAP).

Secondary and exploratory endpoints will be analyzed without adjustment for multiplicity, and all inferential analyses will use a 2-sided 5% significance level. Continuous variables will be analyzed using ANCOVA models and/or repeated measures mixed effect models and dichotomous variables will be analyzed using the same approach as outlined for the primary endpoint. Details of how missing data will be handled for secondary and exploratory endpoints will be provided in the SAP.

Exploratory analyses will be conducted to understand the relationship between exposure and response and details of these analyses will be outlined in the SAP.

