#### **4.3 Per Protocol Population**

The per protocol (PP) population will consist of all subjects in the MITT population who do not have major protocol deviations considered to affect the primary efficacy variable DRSS, have completed their 48-week visit on treatment, and have been at least 70% compliant. The rules for determining exclusion from the per-protocol population will be made and implemented prior to unmasking. Sensitivity analyses of the primary efficacy variables will be conducted using the PP population.

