### 7.2 Descriptive Statistics

For continuous variables, descriptive statistics will include the number of subjects (n), mean, standard deviation (SD), median, minimum and maximum. Categorical variables will be summarized using absolute and relative frequencies (i.e., counts and percentages). For categorical analyses, eyes that receive rescue therapy will be considered as treatment failures. Safety and PK data will be analyzed as collected.

All efficacy data will be summarized by treatment groups and overall using appropriate descriptive statistics. Summaries will be presented for both the MITT and PP populations, where applicable. Due to the small number of subjects enrolled at each center, all summaries and analyses will be performed using data pooled across centers. Unscheduled data, such as information from unscheduled visits or investigator comments, will be included in the data listings. In general, these data will be excluded from the summary tables unless otherwise specified.

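### The only analysis SAP 10.1 labels as sensitivity for the primary endpoint is observed cases in per-protocol completers, and no planned analysis varies the assumption about unobserved Week 48 outcomes

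*SAP*

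**What the plan says.** - **Protocol 11.7** says that the handling of missing primary-endpoint data, "along with sensitivity analyses to assess the impact of missing data will be outlined in the statistical analysis plan (SAP"). It names no method. SAP 1.1 records no change from the protocol, so the commitment stands.
- **SAP 10.1** tests the primary hypotheses in MITT by Fisher's exact test, BID first and QD only if BID is significant. A stratified CMH test is also planned. On missing data it says: "Missing data will be imputed using LOCF; baseline values will not be carried forward".
- **SAP 10.1** names one sensitivity analysis: the same two tests "on OC in the PP population".
- **SAP 4.3** limits PP to MITT subjects without relevant major deviations who "have completed their 48-week visit on treatment, and have been at least 70% compliant".
- **SAP 10** lists what the efficacy analysis will contain, including "Primary Outcome (MITT & PP population, LOCF & OC"). An observed-case run in MITT is therefore planned, although 10.1 neither describes it nor calls it a sensitivity analysis.
- **Rescue:** SAP 7.2 says "For categorical analyses, eyes that receive rescue therapy will be considered as treatment failures". SAP 7.1 adds: "For Observed Case (OC) analyses, results post-rescue are omitted, and last pre-rescue data are carried forward".

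**The concern.** A missing-data sensitivity analysis should keep the population fixed and change what is assumed about the outcomes nobody saw. Observed cases in PP does neither. It selects people who reached Week 48 on treatment, so almost nothing is left to impute. It also moves from MITT to PP at the same time, so a difference from the primary result could not be put down to either change.

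The other planned runs each rest on one fixed assumption. LOCF supposes that an earlier DRSS response persists to Week 48. Observed cases in MITT leaves out non-rescued subjects without a Week 48 grade, in effect treating them as similar to those observed. Nothing counts missing subjects as non-responders, and nothing shows how far the assumption can move before the conclusion changes.

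Few placebo responders are expected, so a small number of missing subjects can matter. The BID comparison is also the gate to QD, so a fragile BID result affects both claims.

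**Working it through.** **1. The plan's own figure.** Inputs from Protocol 11.1 and SAP 3.1: 45 evaluable per arm, 30% versus 5%, two-sided alpha 0.05, Fisher's exact test, 10% non-evaluable.
- Power is the sum, over all outcomes (x, y) with x > y and Fisher p ≤ 0.05, of Bin(x; 45, 0.30) × Bin(y; 45, 0.05). The result is 86.3%, which agrees with the stated figure of more than 85%.
- Enrolment: 45/(1 − 0.10) = 50 per arm. Planned missing: 0.10 × 50 = 5 per arm.

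The sample size is not in dispute.

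**2. What each planned run does with a non-rescued subject who has no Week 48 DRSS**

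| Run | Source | Treatment of that subject |
|---|---|---|
| MITT, LOCF | SAP 10.1 (primary) | Last post-baseline DRSS used |
| MITT, OC | SAP 10 (list only) | Left out |
| PP, LOCF | SAP 10 (list only) | Mostly absent by definition of PP |
| PP, OC | SAP 10.1 (labelled sensitivity) | Mostly absent by definition of PP |

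Within PP, LOCF and OC can differ only in cases such as a missing or ungradable photograph at a completed visit. The only contrast that bears on LOCF is the first row against the second.

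MITT needs only one dose, and baseline is not carried forward. No section says how a subject with no post-baseline DRSS is counted.

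**3. How much the assumption can matter.** The responder counts and the split of missing subjects below are assumptions, not figures from the documents. Five missing per arm is the planned 10%. All p-values are two-sided Fisher. In the tipping rows, missing active subjects are non-responders and k of the 5 missing placebo subjects are responders.

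*About the design rates (14/45 = 31.1%, 2/45 = 4.4%)*
- Observed cases, 14/45 vs 2/45: p = 0.0017
- All missing as non-responders, 14/50 vs 2/50: p = 0.0019
- k = 3, 14/50 vs 5/50: p = 0.040
- k = 4, 14/50 vs 6/50: p = 0.078

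*Smaller effect (11/45 = 24.4%, 2/45 = 4.4%)*
- Observed cases, 11/45 vs 2/45: p = 0.014
- All missing as non-responders, 11/50 vs 2/50: p = 0.015
- k = 1, 11/50 vs 3/50: p = 0.041
- k = 2, 11/50 vs 4/50: p = 0.091

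In the second set, observed cases and non-responder imputation agree, yet two missing placebo responders overturn the result. Only a tipping-point table would show that.

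**The case against.** The strongest reply is that MITT is planned under both LOCF and OC. That comparison holds the population fixed and changes only the missing-data rule, and it can be informative. Suppose 10 BID and 3 placebo responders are observed with 5 missing per arm, and LOCF credits one missing BID subject with an earlier response. LOCF then gives 11/50 versus 3/50, p = 0.041, while OC gives 10/45 versus 3/45, p = 0.069. The two planned tables would visibly disagree. A reader might infer from SAP 10.1 alone that nothing in the plan touches the LOCF assumption; SAP section 10 does not support that. What remains is that this check is complete-case only, is not described or labelled in 10.1, and is the only one.

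Other points in the plan's favour:
- Protocol 11.2.2.2 itself calls the PP analysis a sensitivity analysis, so SAP 10.1 follows it there. Protocol 11.7 does not prescribe non-responder imputation or a tipping point, so leaving them out breaches no named requirement.
- Subjects who stop study medication are to have the full end-of-treatment assessments, including fundus photography, as soon as possible (Protocol 7.6 and 9.3.2.16). LOCF would often carry a grade from discontinuation rather than an older quarterly one. That helps, but a grade after a shorter course is still not a Week 48 outcome.
- Rescue is already covered: rescued eyes are failures in categorical analyses, and the endpoint in SAP 10.1 requires no treatment for PDR or DME in the study eye.
- The tipping scenarios are lopsided. In the smaller-effect case, 2 of 5 missing placebo subjects (40%) respond against 4.4% of those observed, while no missing active subject does.

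These points limit the size of the concern. They do not supply an analysis that varies the assumption.

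**Conclusion.** The concern holds in a limited form. The one labelled sensitivity analysis cannot test LOCF. The unlabelled MITT observed-case run tests it weakly. No planned analysis varies the assumption about unobserved outcomes, so the commitment in Protocol 11.7 is only weakly met.

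The size depends on the effect seen. With 5 missing per arm, a result near the design rates is fairly robust and is lost only under an extreme split. A smaller but nominally significant effect can be lost on two missing placebo subjects, provided no missing active subject responds. These statements rest on assumed counts. A reader might infer that the primary analysis is invalid or that its result would be unreliable; the documents do not support that. The gap is that the reported analyses would not show which of the two situations applies.

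**What to change.** In SAP 10.1:

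1. Name the observed-case analysis in MITT, already listed in section 10, as a sensitivity analysis of the primary endpoint.
2. Add an MITT analysis that counts every subject without a Week 48 DRSS as a non-responder, with all MITT subjects in the denominator. Use the Week 48 window for fundus photographs in SAP Table 2 (Days 295–378) to decide who is missing. Rescued eyes need no new rule here, because SAP 7.2 already makes them failures. This analysis also gives subjects with no post-baseline DRSS a defined place in the count.
3. Add an MITT tipping-point table for each active arm against placebo. It should give the Fisher p-value for every combination of responders among the missing subjects in the two arms.
4. Keep observed cases in PP as supportive.

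The cost is two extra tables from data already collected. The primary test, alpha, testing order and sample size do not change.
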